3.3.4 Subject enrolment

Potentially eligible patients will be screened, investigators should keep a record of subjects who screened for this study. Patients who meet the inclusion criteria will be enrolled. Investigators should keep a record of subjects who entered this study.

The Investigators will:

- Obtain signed informed consent from the potential subject or their guardian/legal representative before any study specific procedures are performed.
- Assign potential subject a unique enrolment number.
- Determine subject eligibility. See Section 3.2.2 and Section 3.2.3

3.3.5 Procedures for handling incorrectly enrolled subjects

Subjects who are enrolled, but subsequently found not to meet the eligibility criteria must be withdrawn from the study. The investigator(s) should record the detailed reasons .

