3. METHODOLOGY

3.1 Study Design

This is a interventional, cluster-randomized, pragmatic clinical study. Totally, there are 41 sites will be selected across China, It is worth mentioning that leading site will directly enter the intervention group, mainly be in charge of supervising and managing the QS implementation in the sites of intervention group. The rest 40 sites will be randomized (stratified by tier levels and geographic region) to the intervention group or control group at the ratio of 1:1. In the intervention group, QS implementation will be performed, and will be checked every 12 weeks. The control group will maintain the current practice. Eligible patients will be recruited and followed up every 12 weeks for 48 weeks.

Eligible consented patients will be enrolled consecutively to minimize selection bias (see section 3.3.2 and section 3.3.3 for inclusion and exclusion criteria).

Figure 1. study schematic

Leading site will directly enter the intervention group, and will recruit at least 27 patients, supervises and manages the QS implementation in the sites of intervention group.

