3.2.2.2 Quality Control (QC) team

Implementation of QS requires input from some clinical staffs of participating hospitals.

The QC team members are recommended to be directors of respiratory departments from participating hospitals and should familiarise themselves with the Quality Standards and core QS components(Figure 2).

The QC team responsibilities include:

- Coordination of overall delivery of the QS
- Facilitate understanding of the overall project objectives and rationale
- Ensure the site-level delivery of QS education and training
- Assess the site-level QS implementation and quality
- Collect feedback of physicians from respiratory departments from participating hospitals

- Regular check implementation performance and review implementation process. This may be achieved by a sub-group in the team who are responsible for ongoing assessment of the programme, and for making recommendations for modifications where necessary.

The QS training will be performed every 3 months by the QC team, the initial one will be a comprehensive face-to-face training and with a full test before sites launch. And the training content of next 3 times during study period will be determined based on the assessment and feedback of implementation sites.

The control group will maintain their usual care. COPD usual care is decided by the physician based on the clinical practice.

Patients in both groups will be trained of exacerbation identification.

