3.4 Criteria for withdrawal

3.4.1 Withdrawal of the informed consent

Patients are free to withdraw from the study at any time, without prejudice to further intervention.

If a subject withdraws from participation in the study, then his/her enrolment code cannot be reused. Withdrawn subjects will not be replaced. Reason of withdrawal will be recorded.

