5. STATISTICAL ANALYSIS PLAN

5.1 Populations for Analyses

The FAS analysis set is all enrolled subjects among all randomized hospitals who had at least one post-baseline efficacy data assessments. The FAS set will be the primary analysis set in the study.

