5.3.2 Analysis of the primary variable (s)

The primary outcome measure is time to CID, which is defined as from enrolment to CID. CID is defined as the first occurrence of any following events over study follow-up:

- ≥ 100 mL decrease in pre-dose trough FEV1
- One moderate-to-severe COPD exacerbation occurring after enrolment
- ≥ 2 -unit increase in CAT total score

Patients who are CID free and alive at the time of analysis will be censored at the date of their last follow-up assessments. Patients who died prior to CID will be censored at the date of death. Patients who withdrew from the study without experiencing an event will be censored at the date of withdrawal.

Time to CID will be analysed using a clustered log-rank test for generation of the p-value and using Breslow approach for handling ties. Hazard Ratio and regarding 95% CI will also be presented. Statistical testing will be conducted at significance level of 0.05.

For each treatment group, time to CID will be summarized using K-M (Kaplan-Meier) method and K-M curves will also be presented.

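### Section 3.3.5 ends follow-up of enrolled patients later found ineligible, so outcome data are lost after allocation and the loss could differ between arms

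*Protocol*

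**What the plan says.** Section 3.3.5 of the Protocol gives the rule: "Subjects who are enrolled, but subsequently found not to meet the eligibility criteria must be withdrawn from the study". The investigator records the reasons, and the section says nothing more.

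Three other places decide what happens to these patients:

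- Section 5.1 defines the FAS, the primary analysis set, as "all enrolled subjects among all randomized hospitals who had at least one post-baseline efficacy data assessments". Meeting the eligibility criteria is not a condition.
- Section 5.3.2 states: "Patients who withdrew from the study without experiencing an event will be censored at the date of withdrawal".
- Section 3.4.1 adds: "Withdrawn subjects will not be replaced". That sentence stands under withdrawal of consent, so applying it to section 3.3.5 is a natural reading but not an explicit one.

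Section 3.3.4 makes eligibility the site investigator's task: "Determine subject eligibility. See Section 3.2.2 and Section 3.2.3". Those two sections describe QS implementation and its monitoring; the criteria are in 3.3.2 and 3.3.3.

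**The concern.** Hospitals are randomised, and patients are enrolled afterwards. Any removal of an enrolled patient is therefore an exclusion after allocation. Four features make that matter here.

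- **Knowledge of allocation.** Section 3.2.2.2 says of the QS training that "the initial one will be a comprehensive face-to-face training and with a full test before sites launch", while for controls "The control group will maintain their usual care. COPD usual care is decided by the physician based on the clinical practice". No blinding of investigators is described. The protocol does not call the trial open; I infer it from this design.
- **Judgement.** One exclusion in 3.3.3 rests on the investigator's opinion about other diseases, including whether they may influence the results. That opinion can be revised once the patient's course is known.
- **Different contact.** Under 6.2.2, intervention visits reassess treatment goals, adherence and inhaler technique, while control visits are data collection only. The occasions on which ineligibility might come to light are not the same.
- **Loose boundaries.** The Synopsis admits patients with CAT of at least 10 or progressive worsening of airflow restriction, and asks for scope to optimise management. Section 3.3.2 requires CAT of at least 10 and does not mention such scope. Who counts as incorrectly enrolled is open to argument.

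At stake is the comparison of all enrolled patients as allocated. Section 3.3.5 instructs sites to stop observing, so no later analysis can recover the data. The sensitivity analysis in 5.3.4 also needs a post-baseline assessment, so it does not help.

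**Working it through.** **What happens to a withdrawn patient.** CAT and FEV1 are measured only at the 12-weekly visits (4.1.1, 4.1.3, Table 1).

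- Withdrawn with no post-baseline efficacy data: outside the FAS.
- Withdrawn with such data and a CID already recorded: in the FAS, and the event counts.
- Withdrawn with such data and no CID: in the FAS, censored at withdrawal.

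An exacerbation recorded before Visit 1 could supply post-baseline data, so an early withdrawal does not always leave the FAS.

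**Inputs from the Protocol (5.2, 3.1, Table 1).** HR 0.70, two-sided 5% level, 80% power, ICC 0.079, medians 121 and 172 days, 40 randomised hospitals, 21 patients each after dropout, 336 days.

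**Assumed inputs.** The protocol gives no rate of incorrect enrolment. Let q be the ineligible share, k their CID hazard relative to the rest, and d the share of them withdrawn at day 0 in an arm.

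**Bias under no true effect.** Let h = ln 2/121 per day for the rest. For an arm with detection d, per patient enrolled:

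- S(t) = (1−q)·exp(−ht) + q(1−d)·exp(−kht)
- f(t) = −dS/dt

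With A the QS arm and B control, the large-sample Cox hazard ratio θ solves the following over 0 to 336 days:

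∫ [ f_A − (f_A + f_B)·θS_A/(θS_A + S_B) ] dt = 0

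For the type I error I use the independent events that give 80% power at HR 0.70, 4(1.960 + 0.842)²/(ln 0.70)² = 246.8, which takes clustering as absorbed by the design effect. The shift is s = |ln θ|·√246.8/2 = 7.855·|ln θ|, and the type I error is Φ(s − 1.96) + Φ(−s − 1.96).

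| q | k | d, QS v control | θ | Type I error |
|---|---|---|---|---|
| 5% | 2 | 100% v 0% | 0.972 | 5.6% |
| 10% | 2 | 100% v 0% | 0.944 | 7.4% |
| 10% | 2 | 75% v 25% | 0.972 | 5.6% |
| 10% | 2 | 60% v 40% | 0.989 | 5.1% |
| 5% | 2 | 60% v 40% | 0.994 | 5.0% |
| 5% | 0.5 | 100% v 0% | 1.037 | 5.9% |
| 10% | 0.5 | 100% v 0% | 1.074 | 8.7% |

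Worked case, second row: |ln 0.944| = 0.0576, s = 0.453, Φ(−1.507) + Φ(−2.413) = 0.066 + 0.008 = 7.4%. The rows with k = 0.5 show that the direction is not fixed: removing low-risk patients from the QS arm works against the intervention.

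**Power.** The stated 713 events do not follow from 247 events times the design effect (2.58 × 247 = 637 at 21 per hospital; 3.054 × 247 = 754 at 27). That is a separate matter. I start from the events expected under the stated medians.

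- Event fractions at 336 days: 1 − 2^(−336/121) = 0.854 and 1 − 2^(−336/172) = 0.742, mean 0.798.
- No extra withdrawal: 40 × 21 × 0.798 = 670 events; design effect 1 + 20 × 0.079 = 2.58; 260 effective events; power Φ(√260 × 0.3567/2 − 1.96) = 82.0%.
- 5% more withdrawn without an event: 19.95 per hospital, 637 events, design effect 2.497, power 81.3%.
- 10% more: 18.9 per hospital, 603 events, design effect 2.414, power 80.5%.

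The loss is 0.7 to 1.5 points.

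**The case against.** The strongest reply is that this is a conventional withdrawal rule and that nothing in the documents shows it acting differently by arm. Most criteria are baseline facts: age, CAT, exacerbation history, FEV1, triple therapy, other trials. The routine sources that would reveal an error are common to both arms: the Table 1 visits, EDC queries, and a data-collecting nurse not involved in recruitment or training (5.4.1). This largely stands, and it limits the size. It does not justify the rule, because the nurse is not said to be blinded or to decide withdrawals, one criterion is a matter of opinion, and visit content differs by arm.

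A reader might go further than the documents allow in four ways.

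- *The 12-weekly QS checks uncover more ineligible patients in intervention hospitals.* The indicators in 3.2.2.3 and Appendix 1 cover treatment, education, inhaler review and vaccine advice. None checks eligibility.
- *The bias is 1/(1 + q(k−1)).* For q = 10% and k = 2 this gives 0.91 and a type I error of about 12%, but it is only the hazard ratio at day 0. About 80% of patients have an event by day 336, so the high-hazard patients leave the risk set and the ratio moves to 0.944.
- *Anyone withdrawn before Visit 1 leaves the FAS.* That holds only without post-baseline efficacy data.
- *There is never a reason to end follow-up.* Section 3.3.2 requires ability to sign consent. Section 3.3.3 excludes patients whom participation may put at risk and those in other interventional studies. Some cases need an exception.

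**Conclusion.** The point holds as a weakness of design. Section 3.3.5 ends observation of patients whom the FAS definition would otherwise keep, and section 5.3.2 treats the loss as ordinary censoring. Withdrawal could depend on arm and prognosis, but this is a risk and not something shown.

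The size is modest and rests on assumed q, k and d. With 5% to 10% ineligible at twice the hazard and all of them withdrawn at day 0 in one arm only, the HR under no effect is about 0.97 to 0.94 and the type I error about 5.6% to 7.4%. At half the hazard the bias runs the other way and is of similar order. With detection closer between arms (60% v 40%) the type I error is 5.0% to 5.1%. The power loss is small beside the 20% dropout already planned. The case for changing the rule is that the loss is avoidable and cannot be repaired afterwards.

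**What to change.** Rewrite section 3.3.5 so that an enrolled patient later found ineligible is recorded as a protocol deviation, with reasons. Outcome data collection then continues to week 48, unless consent is withdrawn or was not valid, or continued participation is itself the concern under 3.3.3. The patient is analysed in the FAS under the hospital's allocation.

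Optionally, add a supportive analysis that leaves out patients who violated 3.3.2 or 3.3.3 on baseline data alone, applied identically in both arms. In the same edit, correct the cross-reference in 3.3.4 to 3.3.2 and 3.3.3.

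The cost is a sentence or two and, if wanted, one extra analysis. The downside is that a few ineligible patients stay in the comparison and slightly dilute the effect.

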3.4 Criteria for withdrawal

3.4.1 Withdrawal of the informed consent

Patients are free to withdraw from the study at any time, without prejudice to further intervention.

If a subject withdraws from participation in the study, then his/her enrolment code cannot be reused. Withdrawn subjects will not be replaced. Reason of withdrawal will be recorded.

4. VARIABLES AND EPIDEMIOLOGICAL MEASUREMENTS

4.1 Efficacy assessments

The primary endpoint is time to CID, time to CID is defined as the time from the date of enrolment until the date of CID, and CID is defined as the occurrence of any of the following events:

- trough FEV1 decline $\geq 100\text{ml}$ or
- CAT increase ≥ 2 unit or
- one moderate or severe exacerbation

4.1.1 Pulmonary Function Tests

All study staff responsible for performing pulmonary function testing should receive standardized training and obtain the qualification certification. All technicians are required to demonstrate proficiency in the use of the equipment and the ability to perform technically acceptable PFTs (ATS criteria, Miller, 2005) prior to performing testing on study subjects. It should be avoided to conduct lung function testing within 6 hours after the use of any short-acting bronchodilators. Ventolin pMDI 400 μg will be inhaled 20 minutes prior to the conduction of reversibility testing.

Lung function test should be assessed at visit 0, visit 1, visit 2, visit 3, and visit 4. Patients do not need to have spirometry at visit 0 if they have lung function test report in 4 weeks before visit 0.

The trough value for FEV1 at Weeks 12, 24, 36, 48 visit is the pre-dose (prior to taking the morning dose of maintenance treatment) and pre-bronchodilator assessment at that visit.

4.1.2 COPD Exacerbations

A COPD exacerbation will be defined as change in the subject's usual COPD symptoms that lasts 2 or more days, is beyond normal day-to-day variation, is acute in onset, and may warrant a change in regular medication.

4.1.2.1 COPD Exacerbation Severity

Each COPD exacerbation will be categorized based on severity as follows:

Moderate: Worsening symptoms of COPD that require treatment with oral/systemic corticosteroids and/or antibiotics.

Severe: Worsening symptoms of COPD that require treatment with in-patient hospitalization.

4.1.4 Patients questionnaire

A patient questionnaire (Appendix 3) will be specifically designed for this study to check the behaviours of physicians in the intervention group. This questionnaire aims to confirm whether the subjects have received the inhaler device usage education, COPD-related disease education, smoking education and advice, and the vaccine advice. Patients questionnaire will perform at the end of every visit.

4.2 Treatment pattern and compliance variables

4.2.1 Treatment pattern

Stable COPD treatment pattern will be described by maintenance treatment(long-acting inhaled medicine prescription and oral medicine prescription) using the following categories. Number of prescription records with each of the following categories will be tracked and reported.

- LAMA (long-acting muscarinic antagonist, e.g. Tiotropium)
- LABA (long-acting beta2-agonist, e.g. Formoterol, Indacaterol, Salmeterol, etc.)
- ICS+LABA (Inhaled corticosteroids + LABA combinations)
- LABA+LAMA
- ICS+LABA+LAMA
- Methylxanthines (long-acting/short-acting)
- SABA (Short-acting inhaled beta2-agonists) or SAMA (short-acting muscarinic antagonist)
- Oral systemic corticosteroids
- Traditional Chinese Medicines
- Antibiotics
- Others(Antitussive/Mucolytics/cough-mucolytics)

4.2.2 Compliance

Treatment compliance will be based upon a percentage of days covered (PDC) calculation of for long-acting inhaled maintenance medication. The PDC will be a measure obtained through the ratio of the cumulative days of drug use and the length of the observation period, expressed as %.

Patients were deemed to be adherent if their PDC was $\geq 80\%$ and not adherent if their PDC was $<80\%$ over the post-index observation period.

5. STATISTICAL ANALYSIS PLAN

5.1 Populations for Analyses

The FAS analysis set is all enrolled subjects among all randomized hospitals who had at least one post-baseline efficacy data assessments. The FAS set will be the primary analysis set in the study.

5.2 Sample size

A total of 1107 patients will be enrolled in the study(41 clusters, 27 patients in each cluster). With 40(20 per treatment group) clusters randomized at a 1:1 ratio (Intervention group: control group) and a size of 27 individuals per cluster (21 after drop out, assuming 20% drop out), approximately 1080 patients will be enrolled **from the 40 randomized hospitals**. In addition, the leading site will be assigned to the intervention group without following the randomization procedure and approximately 27 individuals will be enrolled. **Whilst, data from the leading site will be excluded from the primary analysis set.** The hypotheses are:

$$H_0: S_1(t) = S_2(t) \quad \text{for all } t$$

$$H_1: S_1(t) \neq S_2(t) \quad \text{for some } t$$

If the hazard ratio (HR) for the comparison of QS versus usual care in this patient population is 0.70, assuming ICC is 0.079, 713CID events will provide 80% power to demonstrate a statistically significant difference at a 5% 2-sided significance level (this could translate to an increase of median time to CID from 121 days to 172 days), assuming CID free duration is exponentially distributed.

5.3 Methods for statistical analyses

5.3.1 General Considerations

The statistical analysis plan (SAP) will be finalised prior to data base lock (DBL) and it will include a more technical and detailed description of the statistical analyses described in this section. As randomisation was at the hospital (cluster) level, appropriate statistical methods to account for the clustering effect will be used in the analysis.

Descriptive statistics will be calculated, including n, means, standard deviations, medians, and interquartile ranges for continuous variables and frequency counts and percentages for categorical variables. Percentage will be calculated based on non-missing data unless otherwise specified.

Unless otherwise specified, analyses of change from baseline to a particular time point will be based on the measurement available at that time point. Missing data will be assumed missing at random or missing completely at random. In general, no imputation will be applied unless otherwise specified.

5.3.2 Analysis of the primary variable (s)

The primary outcome measure is time to CID, which is defined as from enrolment to CID. CID is defined as the first occurrence of any following events over study follow-up:

- ≥ 100 mL decrease in pre-dose trough FEV1
- One moderate-to-severe COPD exacerbation occurring after enrolment
- ≥ 2 -unit increase in CAT total score

Patients who are CID free and alive at the time of analysis will be censored at the date of their last follow-up assessments. Patients who died prior to CID will be censored at the date of death. Patients who withdrew from the study without experiencing an event will be censored at the date of withdrawal.

Time to CID will be analysed using a clustered log-rank test for generation of the p-value and using Breslow approach for handling ties. Hazard Ratio and regarding 95% CI will also be presented. Statistical testing will be conducted at significance level of 0.05.

For each treatment group, time to CID will be summarized using K-M (Kaplan-Meier) method and K-M curves will also be presented.

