COPD exacerbation (EMR database definition)	A significant worsening in respiratory symptoms in people with COPD. Either a moderate exacerbation defined as use of systemic corticosteroids and/or antibiotics for at least 3 days; or a severe exacerbation that is an inpatient COPD-related hospitalization or COPD-related death. Exacerbations occurring a minimum of 7 days apart or more will be considered as separate exacerbations.
Diagnosed COPD patient with high exacerbation risk	Patients with COPD who have had 2 or more moderate, or 1 or more severe exacerbations in the last 12 months, AND whose medical record data indicates clearly that there is scope for management optimisation. Patients with frequent exacerbations are at higher future risk of exacerbations. Frequent exacerbations are linked to accelerated lung function decline, greater risk of cardiovascular events and death, and larger healthcare costs. Guidelines state that frequent exacerbators should have their treatment optimised to reduce the risk of future exacerbations and potentially other adverse events. QIP aims to address the management needs of such patients by promoting improved treatment and follow-up.

Patients with scope for management optimisation	High-risk patients who continue to have exacerbations whilst on their current therapy. The intervention will focus on patients whose management may be optimised by correct diagnosis, or where current therapy allows for the addition of at least one inhaled therapy in accordance with GOLD 2022 strategy or national guidelines or where non-pharmacological interventions can be improved.
Quality Standards	The “Chinese Quality Standards of COPD clinical care” (known as the Quality Standards or QS) have been agreed by a panel of 18 experts in COPD, informed by national COPD guideline. There are four evidence-based Quality Standards encompassing identification, clinical assessment, pharmacological and non-pharmacological intervention, and patient follow-up.
Collation of PRO/PRI questionnaire data	At least every 3 months bringing together of PRO/PRI data received during the implementation of the intervention to be used in data analysis and feedback.

RESPONSIBLE PARTIES

Name	Professional title	Role in study	Affiliation	Email address
[name]	Professor of Respiratory Medicine	Primary investigator	Shenzhen People's Hospital	[contact]
[name]	Professor of Respiratory Medicine	Sub-investigator	Shenzhen People's Hospital	[contact]

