5.3.4 Sensitivity analysis

Sensitivity analysis will be conducted among all enrolled subjects who had at least one post-baseline efficacy data assessments.

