Patients in both groups will be encouraged to come back to study hospital once they have COPD related conditions or symptoms worsening. If in emergency case they choose to visit the hospitals other than study hospital, they should report it to study physician or study staffs once it's possible. In case there're data generated from other hospitals that needed to be collected as per this protocol, the data and supportive document (medical record, prescription etc.) will be required on next on-site visit.

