8.7 Collection and Reporting of Adverse Events/Adverse Drug Reactions

For this study, there is no requirement for the patients to use an special investigate medicine, and there is no any safety endpoint. Then no pro-active safety data collection will be taken place. The investigator is responsible for reporting adverse events to regulatory authorities according to China related regulation, i.e. “Provisions for Adverse Drug Reaction Reporting and Monitoring (Order No.81 of the Ministry of Health)”.

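### The protocol gives COPD-related death two statuses in the primary endpoint, counts other deaths nowhere, and plans no comparison of deaths between arms

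*Protocol*

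**What the plan says.** **Primary endpoint.** CID (sections 2.1, 4.1 and 5.3.2) is the first of an FEV1 fall of at least 100 ml, a CAT rise of at least 2 units, or "One moderate-to-severe COPD exacerbation occurring after enrolment". Death is not a component in its own right. The censoring rule in section 5.3.2 is "Patients who died prior to CID will be censored at the date of death".

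**Definition of severe.** There are two. The lexicon of key terms, under its EMR database definition of exacerbation, has "a severe exacerbation that is an inpatient COPD-related hospitalization or COPD-related death". Section 4.1.2.1 has "Severe: Worsening symptoms of COPD that require treatment with in-patient hospitalization".

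**Analysis sets.** The FAS (section 5.1) is "all enrolled subjects among all randomized hospitals who had at least one post-baseline efficacy data assessments". The only sensitivity analysis (section 5.3.4) keeps the same condition: "Sensitivity analysis will be conducted among all enrolled subjects who had at least one post-baseline efficacy data assessments". The first scheduled post-baseline visit is at week 12, which Table 1 shows as Day 90 ± 7.

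**Outcomes and safety.** No primary or secondary outcome in sections 2.1 and 2.2 is mortality. Section 8.7 says "there is no any safety endpoint. Then no pro-active safety data collection will be taken place", while keeping investigator reporting of adverse events to regulators. For care received at another hospital, section 6.2.2 says that "the data and supportive document (medical record, prescription etc.) will be required on next on-site visit".

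**The concern.** The protocol describes these patients as being at raised risk of death and of cardiovascular events (lexicon, sections 1.1 and 1.2), and QS 1 asks sites to assess the risk of both. Treatment is also meant to differ between arms: QS 2 seeks opportunities to change therapy, and section 6.2.2 provides for adjustment at intervention visits only. How death is handled is therefore a substantive question here.

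Two things are at stake. First, the status of COPD-related death in the one formally tested endpoint, and in the severe-exacerbation rate, depends on which section the programmer or site follows. Second, the study aims to show the true benefit of QS (section 2), yet no planned result would change if more patients died in one arm, except to the extent that COPD-related deaths are counted as exacerbations.

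**Working it through.** **1. The sections side by side**

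| Patient dies before any other CID event | Lexicon | Section 4.1.2.1 | Section 5.3.2 |
|---|---|---|---|
| COPD-related, no admission | Severe exacerbation, so a CID event | Not a severe exacerbation | Censored |
| Other cause | Not an exacerbation | Not an exacerbation | Censored |

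The first row is a contradiction. The second is consistent, but leaves these deaths in no outcome.

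**2. Early deaths**

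FEV1 and CAT are scheduled only at visits, so before Visit 1 essentially only an exacerbation can supply post-baseline efficacy data. A patient who dies before then with none recorded fails the condition in section 5.1. Section 5.3.4 repeats that condition and does not bring the patient back.

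**3. How many deaths**

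Inputs from the protocol: 1080 patients from randomised hospitals, 540 per arm; medians of 121 and 172 days; exponential CID-free time; 336 days of follow-up. Assumed: yearly mortality q of 2%, 5% or 10%, equal in the arms; death independent of CID; no dropout.

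- CID hazards: ln 2/121 = 0.005728 per day (control) and ln 2/172 = 0.004030 per day (QS). Their ratio is 0.703, which agrees with the stated HR of 0.70.
- Death hazard: d = −ln(1−q)/365.
- Deaths before CID, per arm: 540 × d/(h+d) × (1 − exp(−(h+d) × 336)), where h is the CID hazard of that arm.

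At q = 5%, d = 0.0001405:
- Control: 540 × 0.02394 × 0.8608 = 11.1.
- QS: 540 × 0.03370 × 0.7537 = 13.7.

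| q per year | All deaths in 336 days | Before CID, control / QS | Before CID, total | Before CID and Day 90 | All deaths before Day 90 |
|---|---|---|---|---|---|
| 2% | 20 | 4.4 / 5.5 | 10 | 4 | 5 |
| 5% | 50 | 11.1 / 13.7 | 25 | 11 | 14 |
| 10% | 100 | 22.5 / 27.6 | 50 | 22 | 28 |

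The Day 90 columns use the same formula with 90 in place of 336, and 1080 × (1 − exp(−90d)). Before-CID-and-Day-90 is probably low, because the model lets any CID occur from day one; the last column is the ceiling.

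**4. Effect on the hazard ratio**

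If death is independent of CID, censoring leaves the CID hazard ratio unbiased, even when the death hazard differs between arms. For CID-or-death the ratio is (QS CID hazard + QS death hazard)/(control CID hazard + control death hazard):

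| q per year | Death hazard equal | Death hazard doubled in QS |
|---|---|---|
| 2% | 0.706 | 0.716 |
| 5% | 0.711 | 0.735 |
| 10% | 0.718 | 0.766 |

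For q = 5%, doubled: (0.004030 + 0.000281)/(0.005728 + 0.000141) = 0.735. Using exactly 0.70 × the control hazard for QS gives about 0.71, 0.73 and 0.76.

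Independence is doubtful. A patient may deteriorate and die between 12-weekly visits with the FEV1 or CAT change unmeasured. If every death before CID followed such an unrecorded deterioration, the hazard ratio that should have been seen would be roughly the one in this table, so the gap from 0.70 indicates the scale of possible bias.

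**The case against.** **Death is not ignored throughout.** A reader might infer that death never counts against either arm. The documents do not support this: under the lexicon a COPD-related death is a severe exacerbation. This turns the point into one of contradiction. One could reply that the lexicon entry governs only EMR data, but section 3.2.4 names the EMR as a source for this trial, so both definitions can apply to the same patient.

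**Deaths would not be invisible.** A reader might infer from section 8.7 that a fatal harm would go unseen. Passive reporting to regulators remains, and the censoring rule itself needs dates of death. Enrolment is logged (section 3.3.4), and section 6.2.2 asks for emergency care elsewhere to be reported as soon as possible. What is missing is a comparison by arm. Nor is COPD hospitalisation missed, since its rate by arm is a secondary outcome.

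**Censoring does not by itself favour the arm with more deaths.** A reader might infer that it does. Under independence it removes events and time at risk together. Dropping early event-free deaths from the FAS would, if anything, slightly raise that arm's CID hazard. Bias needs dependence between death and CID, which is plausible but which the protocol gives no figure to size.

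**Exclusion from the FAS is not automatic.** An exacerbation captured from the EMR or charts before death might qualify the patient. Section 5.1 does not settle this, so the exclusion applies only where no efficacy data exist.

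**The SAP may hold more.** Section 5.3.1 defers technical detail to it, and a death-as-event sensitivity analysis could sit there. That is fair as to detail. But the censoring rule, both definitions of severe and the condition on the sensitivity set are fixed in the protocol and need correcting there.

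**Conclusion.** The point holds as an inconsistency in the confirmatory endpoint together with a gap in planned reporting. COPD-related death is an event under the lexicon and a censored time under section 5.3.2, with section 4.1.2.1 on the second side. Other deaths enter no outcome. Early deaths without efficacy data are in neither analysis set, and no comparison of deaths between arms is planned.

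The effect on the primary estimate is modest: none under independence, and a shift from 0.70 to about 0.72, 0.73 or 0.77 if the death hazard doubled in the QS arm and every death before CID were counted. These figures rest on assumed mortality of 2%, 5% and 10% a year, constant hazards and no dropout; with the planned 20% dropout the counts would be smaller. The greater weakness is that even doubled mortality from causes other than COPD would alter no planned result. This should be corrected, but it does not undermine the design.

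**What to change.** 1. Reconcile the lexicon, section 4.1.2.1 and section 5.3.2 so that COPD-related death has one status, applied alike to the CID endpoint and the severe-exacerbation rate.
2. In section 5.3.4, specify a sensitivity analysis of the primary result that counts all-cause death before CID as an event at the date of death, in all enrolled patients of the randomised hospitals, including those who die before Visit 1.
3. Record vital status (date and cause) in both arms, from hospital records or by telephone when a patient does not attend, and report deaths by arm in that same population.

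The cost is protocol wording, one small data item and one table; the date of death is already needed for censoring. The drawback is that some events in the sensitivity analysis will be deaths unrelated to COPD.

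Making death an event in the primary definition, or collecting all-cause hospitalisation, are optional design choices and are not needed to close this point.
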